7.3 Protocol deviations

Important protocol deviations identified will be summarized based on safety set.

A listing will include all important deviations identified based on data recorded and/or protocol deviation logs. Additional listings will be provided for the details of subject's visit impact due to Corona Virus Disease of 2019 (COVID-19).

7.4 Demographics and background characteristics

7.4.1 Demographics

Demographic variables age (months), adjusted age (months), at baseline will be summarized descriptively. Age category (<2 years, ≥ 2 years), sex, race, ethnicity and country will be summarized using count and percentage.

7.4.2 Baseline disease characteristics

The following baseline variables from the double blind study (XPF-009-301) will be summarized using descriptive statistics or counts and percentage.

Subjects experience >= 1 seizure per day in the month prior to screening Number of seizures per month (28 days) prior to screening Diagnostic KCNQ2 genetic testing details

- o Zygosity
- Genetic test classification

Subjects with vagus nerve stimulation therapy (Yes/No)

Pre-study seizure type (Pre-study Seizure Type and Description CRF page)

Listings will be provided for all information captured in CRF for seizure diagnosis and treatment history, diagnostic KCNQ2 genetic testing, vagus nerve stimulation therapy, pre-

study seizure type and description.

7.4.3 Concomitant medications

Medications will be coded to a preferred term and an Anatomic Therapeutic Classification (ATC) code by using the latest available version of the World Health Organization Drug Dictionary Enhanced (WHODDE).

Concomitant medications: are defined as any medications taken between first dose of study treatment (inclusive) in OLE and last dose of study treatment (including taper period). If any medication started prior to first dose in OLE and are ongoing or ended after first dose in OLE are also considered as concomitant.

Concomitant medications will be summarized descriptively using frequency tables by ATC class 2 and preferred name.

Listing will be provided for concomitant medication.

7.4.4 Concomitant procedures

Concomitant procedures (Surgical or Non-Surgical) will be presented in a listing only.

7.5 Extent of exposure

7.5.1 Treatment duration

Duration of study drug (in days) in OLE will be calculated as: last dose date – first dose date in OLE+ 1 day, regardless of study drug interruption.

Duration of study drug exposure and total dose (sum of all dose administered) administered will be summarized descriptively using safety set.

7.5.2 Treatment compliance

Study drug compliance based on the number of capsules taken will be calculated as:

```
\frac{[\text{total number of doses dispensed - (total number of doses returned, lost or damaged)]}{\text{Sum (planned doses per day × days of the planned dose in period)}} \times 100
```

Descriptive summary for study drug compliance using safety set. They will also be summarized in categories "<80%", "80% to 100%" and ">100%" using frequency tables. Study drug administration details will be listed.

7.6 Efficacy analyses

7.6.1 Analysis of key efficacy endpoint

Analysis of the key efficacy endpoint based on key efficacy analysis set.

Statistical Analysis Plan (SAP) 🔀 🗙 E N O N

The difference between XEN496 and placebo in monthly seizure frequency among subjects who were randomized to placebo in the main study will be analyzed using a Wilcoxon signed-rank test with 2-sided significance level of 5%. The estimated pseudo-median intrasubject difference in seizure frequency will be provided with corresponding 95% CI (2sided) based on Hodges-Lehmann method.

Descriptive summary will be provided for average monthly (4-week) seizure frequency collected from motor seizures described above. Individual listings will also be provided.

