1 INTRODUCTION

The purpose of this Statistical Analysis Plan (SAP) is to provide detailed descriptions of the statistical methods, data derivations and data displays for study protocol XPF-009-302 Version 3.0, "An open-label extension study of XEN496 in pediatric subjects with KCNQ2 developmental and epileptic encephalopathy" dated 09 May 2022 for final analysis. The table of contents and templates for the tables, figures and listings (TFLs) will be produced in a separate document.

Any deviations from this SAP will be described and justified in the Clinical Study Report (CSR).

The preparation of this SAP has been based on International Conference on Harmonization (ICH) E3 and E9 guidelines.

2

examinations,

Objectives Endpoints **Primary** To assess the long-term safety and Severity and frequency of adverse • tolerability of XEN496 in pediatric subjects events (AEs) and serious adverse with KCNQ2 developmental and epileptic events (SAEs); clinically significant encephalopathy (KCNQ2-DEE) who had changes in laboratory tests, vital signs, electrocardiograms (ECGs), physical participated in the primary study (XPF-009neurologic 301). and CI

STUDY OBJECTIVES AND ENDPOINTS

Secondary

Secondary	
To evaluate the intra-subject efficacy of XEN496 in reducing seizure frequency compared to prior placebo treatment in pediatric subjects with KCNQ2-DEE who were previously randomized to receive placebo in the primary double-blind Phase 3 study (XPF-009-301).	• Change in monthly countable motor seizure frequency, comparing the first 15 weeks of XEN496 treatment in the open label extension (OLE) study to the seizure frequency reported during treatment in the preceding primary study (XPF-009-301), among only those subjects who were randomized to the placebo arm in the primary study (XPF-009-301). (key efficacy endpoint)
To assess the long-term effect of XEN496 on seizure reduction in pediatric subjects treated with XEN496.	 Change from pre-randomization baseline in the previous study over time based on response categories (<25%, 25 to <50%, 50 to <75%, 75 to <100%, 100%), based on estimated seizure frequency every 3 months during the OLE period. Percent change from baseline in countable motor seizure frequency, relative to pre-randomization baseline of the previous study (XPF-009-301), assessed over time every 3 months during the OLE.

Statistical Analysis Plan

Objectives	Endpoints			

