3 STUDY DESIGN

3.1 General study design

This is a Phase 3, open-label, long-term extension study to evaluate the safety, tolerability, and efficacy of XEN496 administered as adjunctive therapy in pediatric subjects with KCNQ2-DEE who participated in the primary study, XPF-009-301.

Approximately 40 subjects may be included in the study based on the anticipated number of subjects who could roll over from Study XPF-009-301.

Subjects will undergo the following:

- Screening/Baseline period Subjects will undergo eligibility assessment at Visit 22 or early termination in the primary study (XPF-009-301).
- Treatment period 36 months:
 - Blinded transition/titration period
 - Open-label period approximately 35 months.

Subjects who received XEN496 in the primary study will continue to receive XEN496 at the same dose throughout the OLE.

[figure not shown]
Subjects allocated to placebo in the primary study will be required to begin a titration of XEN496 CCI

- CCI
- Taper period CCI
 Subjects who discontinue or complete the study treatment will be required to taper off study drug CCI
 The actual duration of the taper period will depend on the subject's dosage prior to taper.
 - Follow-up Approximately 4 weeks after subjects have tapered off of study drug.

Total study duration per subject is estimated to be 37 months.

The Study Design Schematic is presented in Figure 1.

Figure 1: Study Design Schematic

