3.2 Randomization and blinding

[figure not shown]
This is an open label study and randomization is not applicable.

A double-blind transition/titration period will be used to maintain blinding to the treatment allocation in the primary study (XPF-009-301). During this period, treatment will be administered under double-blind conditions: Subjects and their caregivers, the investigators, and the outcomes assessor will be blinded to treatment assignment.

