5.3 Key Efficacy Analysis Set

The key efficacy analysis set includes those subjects who were treated with placebo in the preceding primary study (XPF-009-301) and switched to XEN496 treatment in the current study, with at least 4 weeks of evaluable seizure data in both study periods.

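### The key seizure test always puts placebo before XEN496, so it cannot separate drug effect from time or open-label reporting; a drift check in XEN496 Only subjects should be added

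*SAP*

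**What the plan says.** - **Endpoint (SAP Section 2).** The key efficacy endpoint contrasts each subject's 28-day rate of countable motor seizures across the two studies: "comparing the first 15 weeks of XEN496 treatment in the open label extension (OLE) study to the seizure frequency reported during treatment". The earlier period is the one spent on treatment in XPF-009-301, the primary study. Only subjects randomized to placebo there are included.
- **Analysis set (SAP Section 5.3).** It holds "subjects who were treated with placebo in the preceding primary study (XPF-009-301) and switched to XEN496 treatment in the current study", with a minimum of four weeks of usable diary data in each period.
- **Test (SAP Section 7.6.1).** The quantity is labelled "The difference between XEN496 and placebo in monthly seizure frequency among subjects who were randomized to placebo in the main study". The method is a "Wilcoxon signed-rank test with 2-sided significance level of 5" percent. For estimation, the section says: "The estimated pseudo-median intrasubject difference in seizure frequency will be provided". A Hodges-Lehmann 95% CI goes with it.
- **Blinding.** SAP Section 3.2: "A double-blind transition/titration period will be used to maintain blinding to the treatment allocation in the primary study". The protocol synopsis gives this period 24 days and says that all roll-over subjects receive active XEN496.
- **The other group (SAP Section 3.1).** "Subjects who received XEN496 in the primary study will continue to receive XEN496 at the same dose throughout the OLE". Section 3.3 adds that they have no further titration, and allows dose adjustment if required.
- **Other analyses.** The only sensitivity analysis named for this endpoint (SAP Section 6.2.1) concerns missing data. Section 7.6.2.1 summarises percent change from the pre-randomization baseline in 3-month blocks, including combined data from both studies by primary-study group, descriptively.

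**The concern.** The label in Section 7.6.1 claims more than the design identifies. What is computed is extension minus primary study. It equals XEN496 minus placebo only if nothing else differs between the two periods, and the documents point to several things that can differ:

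- **Reporting.** The outcome is a caregiver diary, and every child is on active drug in the extension. The 24-day blind protects the primary-study allocation. It does not hide that XEN496 is being given, so expectation can start at entry.
- **Regression to the mean.** The synopsis counts subjects withdrawn from the primary study for protocol-defined worsening as completers, so they may roll over. A placebo period that ended on a high stretch tends to be followed by a lower one.
- **Time and co-treatment.** Seizure rates may drift with age. Change in background antiseizure medication is itself a study objective (SAP Section 2), and the key analysis does not account for it.

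This is the only hypothesis test named in the visible SAP. Its 5% error rate does not protect the claim that will be read from it.

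**Working it through.** **1. What the test estimates.** On the log scale, for former placebo subjects (P):

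OLE_P − 301_P = drug effect + time trend + reporting shift + regression to the mean.

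The order is the same for all, so these terms cannot be separated within the group. Share of the 15 weeks (105 days) that is blinded: 24/105 = 23%. Open-label: (105 − 24)/105 = 81/105 = 77%.

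**2. The plan's own figures.** SAP Section 4 expects up to about 40 subjects and gives no power, effect size or SD, so there is no calculation to reproduce. The exact two-sided size of the signed-rank test is 0.0488, 0.0479 and 0.0484 for n = 10, 15 and 20. The nominal 5% is therefore right when nothing but treatment changes.

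**3. Size under drift.** These inputs are assumed and not in the documents: 20 per group, 105 days per period, Poisson counts, median 30 seizures per 28 days, between-subject log-SD 0.8, no drug effect, and a 20% decline common to both groups. The period SD is an independent log-scale deviation in each period, so the SD of a subject's log ratio is √2 times as large (0.28 to 0.99).

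| Period SD | Favourable significant result, signed-rank (nominal 2.5%) |
|---|---|
| 0.2 | about 77% |
| 0.3 | about 48% |
| 0.5 | about 21% |
| 0.7 | about 12% |

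Repeat runs differ by up to about two percentage points. A second simulation on different assumptions (lognormal rates, log-ratio SD 0.5, n = 20) gives two-sided rejection of 6%, 8%, 29% and 65% for a decline of 0, 10%, 20% and 30%. At 20% decline it ranges from 8% to 73% over n = 10 to 20 and log-ratio SD 0.8 to 0.3.

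Drift can also hide an effect: a true 20% reduction with a 25% upward drift gives 0.80 × 1.25 = 1.00, no change.

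**4. What XEN496 Only subjects (X) add.** They cross the same two periods with no planned switch of drug. The contrast is

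[OLE_P − 301_P] − [OLE_X − 301_X] = [301_X − 301_P] + [OLE_P − OLE_X].

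Drift common to both groups cancels. In step 3 the between-group rank test stays near 2.5% favourable. In the second simulation it stays at 3.4% to 5.7% two-sided (nominal 5%). Unequal drift does not cancel. With no drug effect and period SD 0.3:

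- 20% versus 10% decline: a ratio of 0.80/0.90 = 0.89 remains, and the favourable false-positive rate is about 12%.
- 20% versus 0%: a ratio of 0.80 remains, and the rate is about 32%.

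On the right-hand side, both groups take XEN496 in the extension, so apart from titration the last bracket should be near zero. The contrast is then mainly the randomized primary-study comparison.

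**5. Titration.** Dosing within the primary study is not described. Suppose 24 of its 105 days were titration with no effect, and full effect is a 50% reduction. The XEN496 Only primary-period average is (24 × 1 + 81 × 0.5)/105 = 0.614 of the untreated rate. Their extension rate is 0.5, so they show 0.5/0.614 − 1 = −19% with no drift at all. With half effect during titration: (24 × 0.75 + 81 × 0.5)/105 = 0.557, and 0.5/0.557 − 1 = −10%. Either way the contrast understates the effect.

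**6. Precision.** With the step 3 inputs, period SD 0.3, no drift and a true 35% reduction, power is about 95% (signed-rank) versus 79% (between-group). If titration removes 12% of the effect in each group's first XEN496 period (0.35 × 0.88 = 30.8%), it is about 87% versus 49%.

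**The case against.** The strongest reply is that the within-subject change is the stated objective, so the test does what it was meant to do, and that the by-group 3-month summaries already display XEN496 Only subjects across the transition. The first part stands: the fault lies in attribution, and the test should stay. The second stands only in part. Those summaries are relative to the pre-randomization baseline, do not match the 15-week window, and give no between-group difference or CI.

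It is also fair that the comparator is imperfect. Reporting shift need not be equal when only one group switches treatment. Roll-over after worsening may differ by arm. Dose and background medication can change in XEN496 Only as well. The contrast largely restates the primary-study comparison. All of this stands and limits what the check can show.

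Stronger readings that a reader might infer, and that the documents do not support:

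- *The between-group contrast separates drug from time.* It does so only for equal drift, and it is not independent evidence.
- *The key result will be falsely favourable.* No drift rate, SD or allocation ratio is given, and drift may run either way.
- *This is the only p-value in the plan.* Section 6.2.1 plans imputation analyses of the same endpoint, and the adverse-event analysis text is not visible.
- *The trial's main conclusion is at risk.* The primary objective is safety.

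**Conclusion.** The confounding is real and follows from the design. The one-sample test in a fixed order cannot tell XEN496 from a time trend, regression to the mean or a reporting shift, and the visible SAP neither says so nor checks it. Protocol Section 8.3.3 appears in the contents but its body is not visible, so the gap is established for the SAP only.

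The size is illustrative. For a 20% non-drug decline with 20 per group, the favourable false-positive rate is roughly 12% to 77% over period SDs of 0.7 to 0.2, against 2.5%. Every input to that range is assumed. The direction of the conclusion does not depend on them; the figure does. A supportive check on data already collected is a cheap improvement. It does not replace the key analysis.

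**What to change.** Keep the signed-rank test as the key analysis and add to SAP Section 7.6.1:

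1. **A parallel set to 5.3:** XEN496 Only subjects with at least four weeks of evaluable diary data in both periods. The set in Section 5.4 is not enough, because it asks for only one evaluable record per period.
2. **The same change in that set:** first 15 extension weeks versus the primary-study treatment period. Use the log ratio of 28-day rates with a stated zero rule (for example, a small constant added to both rates), or percent change. Seizure freedom is a planned response category, so zeros must be handled. Absolute differences scale with the starting rate and are not suitable here.
3. **The report:** each group's change, and the Hodges-Lehmann between-group shift with 95% CI, beside the key result.
4. **The interpretation:** the within-group result alone does not separate drug from time or unblinding. The between-group contrast removes only common drift, draws mainly on the randomized primary-study comparison, and may understate the effect if the primary-study XEN496 period includes titration.

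Cost: one extra set definition, one derivation and one table, with no new data. The contrast is less precise than the key test, so it should be labelled supportive and carry no decision rule.

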7.6.2 Analysis of additional efficacy endpoints

Analyses of additional secondary efficacy endpoints will primarily be descriptive based on the secondary efficacy analysis set.

For the summary of data from the OLE only, a combined treatment group including those subjects treated in OLE will be included. For the summary of endpoints with a combined database from both the primary study (XPF-009-301) and the OLE study, the data will be presented by treatment group in the primary study (XPF-009-301). Data after switching from placebo to XEN496 will be clearly identified.

7.6.2.1 To assess the long-term effect of XEN496 on seizure reduction in pediatric subjects treated with XEN496

- Change from pre-randomization baseline (double blind baseline, refer Section 7.1) in the previous study over time based on response categories (<25%, 25 to <50%, 50 to <75%, 75 to <100%, 100%), based on estimated seizure frequency every 3 months during the OLE period. Proportion of subjects achieving a reduction in 3 months (90 day) seizure frequency from baseline of <25%, 25% to <50%, 50% to <75%, 75% to <100%, and 100% will be summarized using count and percentage. (refer section 6.1.1 for details).
- Descriptive summary will be given for percent change from baseline in countable motor seizure frequency, relative to pre-randomization baseline of the previous study (XPF-009-301), assessed over time every 3 months during the OLE.
- Descriptive summary will be provided for percent change from baseline in countable motor seizure frequency, relative to pre-randomization baseline of the previous study (XPF-009-301), for every 3 months based on combined data from both XPF-009-301

and the OLE, by the treatment group in the previous study.

7.6.2.2 To evaluate Caregiver Global Impression of Severity (CaGI-S) and Caregiver Global Impression of Change (CaGI-C) scores

The CaGI-S for overall condition and seizure severity will be summarized at baseline (OLE Baseline and double-blind baseline) and each of the post-baseline visit using number and percent. Change from baseline (OLE Baseline and double-blind baseline) to post baseline will also be summarized.

The CaGI-C will be summarized at each of the post-baseline visit using counts and percentage for the following domains: overall condition, seizures, behavior, alertness, motor skills, visual function, and communication.

Listings will be provided for CaGI-S and CaGI-C scores.

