5.4 Secondary Efficacy Analysis Set

The secondary efficacy analysis set includes those subjects who were treated in both the preceding primary study (XPF-009-301) and the current OLE study, with at least 1 evaluable seizure data in both study periods.

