6.1.1 Efficacy Variables

6.1.1.1 Seizure frequency

Caregivers will record all countable motor seizures in the daily seizure diary, which will be reviewed at selected visits as specified in Table 2 and Table 3. The following motor seizures with a duration of at least 3 seconds will be recorded in the seizure diary:

[figure not shown]
- Focal tonic.
- Focal motor.
- Focal with secondary generalization.
- Generalized tonic.
- Focal clonic.
- Generalized clonic.
- Generalized tonic-clonic.

[figure not shown]
Important exclusions to the countable seizures are:

- Single myoclonic jerks.
- Staring spells without a motor component.

If epileptic spasms are suspected or reported, the investigator must be contacted immediately to confirm the diagnosis and to initiate treatment.

The denominator will be based on those evaluable days when an entry of yes or no is provided on occurrence of seizure of any type. Days with counts of 0 seizure will be included in the denominator; while days with missing seizure counts will be excluded from the denominator.

The average monthly seizure frequency (per 28 days) will be derived with the formula below:

sum of daily countable seizure counts reported during the placebo (or XEN496) treatment period

Total number of days within the time period when seizure data is reported $\times 28$

Percent change of average monthly seizure frequency will be derived using the below formula where *average monthly seizure frequency* is defined as above and *Baseline* refers to the comparator period appropriate for the endpoint (eg. placebo period for the key efficacy endpoint and the pre-randomization baseline period for other efficacy endpoints):

Average monthly seizure frequency – Baseline average monthly seizure frequency Baseline average monthly seizure frequency × 100

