6.2 Handling of missing data and outliers

6.2.1 Missing data analysis methods

The key efficacy endpoint of seizure frequency will be derived from the days with nonmissing seizure data as described in Section 6.1.1. To assess the impact of missing data due to early dropout, sensitivity analysis incorporating missing data multiple imputations with both missing at random (MAR) and missing not at random (MNAR) mechanisms. Details of the analysis will be specified in the analysis section 7.6.1..

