7 STATISTICAL METHODS

7.1 General statistical conventions

All statistical procedures will be completed using SAS GRID Linux/SAS Studio version 9.4.

Unless otherwise stated, all statistical testing will be two-sided and will be performed using a significance (alpha) level of 0.05. Two-sided 95% confidence intervals (CI) will be provided when relevant.

Continuous variables will be summarized using descriptive statistics, including number of subjects (n), mean, geometric mean (for efficacy endpoints only), first quartile (Q1), median, third quartile (Q3), standard deviation (SD), minimum and maximum.

Categorical variables will be summarized using frequency counts and percentages in each category. The denominator for all percentages will be the number of subjects in that treatment group within the population of interest, unless otherwise noted. Percentages will be rounded to one decimal place.

For summary purposes, baseline will be defined as the last available OLE pre-dose value; all summaries will be presented by treatment group assigned in the double blind study (XPF-009-301) and overall, unless otherwise specified.

➢ XEN496 Only

(Subjects who received XEN496 in the primary study and continue to receive XEN496 at the same dose throughout the OLE)

Placebo to XEN496

(Subjects allocated to placebo in the primary study and received XEN496 in OLE)

> Total

All subject data, will be presented in individual subject data listings. Unless otherwise stated, unscheduled visit results will be included in date/time chronological order, within subject listings only. The treatment group as well as subject's sex and age will be stated on each listing. Unless otherwise stated, data listings will be based on all enrolled set.

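### The 3-month percent-change summaries in SAP 7.6.2.1 cannot separate a change in effect from a change in which children still contribute data

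*SAP*

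**What the plan says.** Section 7.6.2.1 of the SAP states: "Descriptive summary will be given for percent change from baseline in countable motor seizure frequency, relative to pre-randomization baseline" of the primary study, "assessed over time every 3 months during the OLE". A further summary does the same on data combined across the two studies, and a response-category table accompanies them. With 36 months of treatment (SAP 3.1) there are 36 / 3 = 12 windows in the OLE.

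Four provisions decide who is in each window:

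- **Type of analysis (7.6.2).** "Analyses of additional secondary efficacy endpoints will primarily be descriptive based on the secondary efficacy analysis set". No longitudinal model is named.
- **Analysis set (5.4).** Entry requires treatment in both studies, "with at least 1 evaluable seizure data in both study periods". There is no retention rule and no minimum of data per window.
- **Frequency formula (6.1.1.1).** "days with missing seizure counts will be excluded from the denominator". A child with no diary days in a window has no frequency for it.
- **Missing data (6.2.1).** The section opens with the key endpoint: "The key efficacy endpoint of seizure frequency will be derived from the days with nonmissing seizure data". It continues: "To assess the impact of missing data due to early dropout, sensitivity analysis incorporating missing data multiple imputations", under both missing-at-random and missing-not-at-random assumptions. Details are deferred to 7.6.1, whose visible text has none. The key endpoint covers only the first 15 weeks of OLE treatment.

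For percentages, 7.1 sets a default: "The denominator for all percentages will be the number of subjects in that treatment group within the population of interest". It also lists n among the statistics for every continuous variable. Section 7.2 tabulates discontinuations and their reasons, without linking them to seizure response.

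**The concern.** The SAP does not call these summaries observed-case, but that is what the formula produces when no other rule is given. Each window then describes a different group of children. A reader comparing Month 3 with Month 36 sees two things at once: any change within children, and any change in which children remain. Nothing specified for these summaries pulls them apart.

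The objective is the long-term effect on seizure reduction, so the shape of this series is what a reader will look at. Three years of open-label treatment leave room for attrition. Poor responders can be present from the start: the protocol synopsis (inclusion criterion 1) treats a child who left the primary study for protocol-specified worsening as having completed it. If such children left the OLE sooner, a flat effect would look like a growing one. If better responders left sooner, a flat effect would look like a waning one.

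**Working it through.** The documents give no dropout rate, expected effect or variance for this endpoint, so there is no planned figure to reproduce. The check asks how far the planned summary moves when the truth does not move.

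**1. Arithmetic example (assumed).** Twenty children are constant at -60% and twenty are constant at 0%. If k of the children at 0% leave, the mean among those remaining is -60 × 20 / (40 - k).

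| k | Mean percent change |
|---|---|
| 0 | -1200/40 = -30.0% |
| 4 | -1200/36 = -33.3% |
| 8 | -1200/32 = -37.5% |
| 12 | -1200/28 = -42.9% |
| 16 | -1200/24 = -50.0% |

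If 8 of the children at -60% leave instead, the mean is -60 × 12 / 32 = -22.5%. No child has changed in any row.

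**2. Simulation.** From the documents: about 40 subjects (SAP 4) and 12 windows. Assumed: each child's log rate ratio to baseline is drawn once from Normal(log 0.65, SD 0.8) and stays fixed; within-window noise has SD 0.25 on the log scale; a poor responder has less than 25% reduction; exit is possible between consecutive windows, 11 times in all; 2,000 replicates. The median at window 1 is about -34% in every scenario.

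| Exit per quarter, poor / other | Median at window 12 | n left |
|---|---|---|
| 5% / 5% (unrelated) | about -33% | 23 |
| 2% / 1% | about -37% | 34 |
| 5% / 2% | about -41% | 28 |
| 10% / 2% | about -50% | 23 |
| 20% / 5% | about -57% | 13 |
| 2% / 10% (reversed) | about -5% to -8% | about 21 |

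For the unrelated case, n can be checked directly: 40 × 0.95^11 = 22.8. Repeat runs differ by about a point, and by a little more in the reversed case, which depends on whether exit follows the observed or the underlying response.

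**3. Do the proposed displays remove the false trend?**

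- *Same children at both ends.* At 10%/2%, the children present at window 12 have a median of about -50% at window 1 and -50% at window 12. At 20%/5% they are at about -57% at both. The trend disappears, but the level is that of stayers, not the true -34%.
- *Last available window, every child.* The median is about -30% at 10%/2% and -28% at 20%/5%. There is no false growth, and the effect is slightly understated because a child tends to exit after a bad window.

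**4. A second model.** Here the true median is about -40%, the between-child SD is 0.8, and the exit hazard is logistic in the last window's log ratio. With 40% cumulative exit and slope 0.7 per SD, the planned median goes from -40.1% to -51.9%, while the children still present at window 12 go from -52.2% to -51.9%. At least 10 points of false growth appear in 55% of trials of 40 (77% at slope 1.5), against 17% when exit is unrelated to response. With 10% cumulative exit, across both slopes and between-child SDs of 0.5 and 0.8, the drift is only about 2 to 5 points. With slope -0.7 and 40% exit the median moves to -25.0%.

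**5. The response table.** At 10%/2%, the share with at least 50% reduction, over a fixed denominator, falls from about 38% to 29% because children without data sit in no category. In that scenario this table falls while the median percent change appears to improve.

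**The case against.** The strongest reply is that a reader might infer a bias in favour of XEN496, and the documents do not support that. They give no exit rate and no link between exit and response. Children may also leave for tolerability. With unrelated exit the series is flat, with low attrition the drift is a few points, and with the reverse pattern it runs against the drug. This stands in full: the point is conditional, and no direction can be asserted.

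Much of the needed information is already planned. Section 7.1 requires n, 7.2 tabulates discontinuation and its reasons, and individual data are listed. A fall from 40 to 23 would be visible. That stands too, but n shows how many left, not whether they were the poor responders.

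The fixed-denominator response table is a conservative counterpart, and a divergence between the two displays would itself hint at attrition. This is fair. A reader might take the response table to be inflated as well; under the 7.1 default it is not. What it lacks is a row accounting for the missing children.

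The protocol's contents list 8.3.4 on additional efficacy endpoints and 8.3.5 on handling of missing data, but neither text is in the public copy. The statement that no method is specified therefore applies to the visible SAP text only.

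Finally, a constant cohort is a completer analysis. Suppose half the children lose response at a random window (log ratio up by 0.8). The full-cohort median worsens by 33 points (-34% to -1%). The Month-36 constant cohort shows only 21 points (-50% to -29%) at 10%/2% exit and 9 points (-68% to -59%) at 40%/2%. This stands, and it rules out resting durability on that cohort.

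**Conclusion.** The point holds conditionally. On the visible SAP text, the 3-month percent-change summaries use whoever has diary data in the window, and nothing specified for them distinguishes a changing effect from a changing group. If exit depends on response, the window-12 median can depart from a constant -34% by about 3 points (2%/1% per quarter) to about 23 points (20%/5%) towards apparent growth, or by more than 25 points the other way if better responders leave. If exit is unrelated to response there is no systematic drift. All exit rates, the response distribution and the noise level are assumptions.

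Two stronger conclusions are tempting and do not follow. One is that the plan will overstate durability: that needs an exit pattern the documents do not describe. The other is that the constant cohort gives the right answer: it removes the false trend when responses are constant, but hides waning when children who lose response leave.

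The consequence is bounded. These are untested descriptive summaries in an extension study whose primary objective is safety. A repair is still worthwhile because they are the main evidence on a stated secondary objective. One limit of the repair: for the OLE-only summaries 7.6.2 combines both prior-treatment groups, so the first window includes former placebo subjects in titration. A rise from that source is not attrition, and a constant cohort will not remove it.

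**What to change.** In SAP 7.6.2.1:

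1. Add, as a supportive display, the same percent-change summary in constant cohorts: subjects with data through Month 12, through Month 24 and through Month 36. Label it as describing stayers only.
2. Add, as a supportive display, each subject's last available 3-month window for all subjects in the secondary efficacy analysis set.
3. Add a row for discontinued or no data to the response-category table, so that the fixed denominator of 7.1 sums to 100% at each window.
4. State that the effect will not be described as maintained or growing from the window-by-window series alone. It is to be read with displays 1 and 2, and durability is not to rest on the constant cohort alone.

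No change is needed to obtain n per window, which 7.1 already requires. If protocol 8.3.5 contains a rule for these endpoints, cite it in 7.6.2.1.

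The cost is a few extra descriptive tables from data already collected. Late constant cohorts will be small (13 to 23 children at Month 36 in the two heavier poor-responder exit scenarios), and the last-window summary can slightly understate the effect (about -30% or -28% against a true -34% in those scenarios).
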